#### **5.4 Special Treatment Considerations. Dose Adjustments of Study Drug**

All dose modifications should be based on the worst preceding toxicity.

Every effort should be made to administer study treatment on the planned schedule. However, in the event of significant treatment-related toxicity, administration of study drug could be interrupted or delayed as described in the following sections.

##### **5.4.1 Dose Interruption**

In the event of significant treatment-related toxicity, Blissel® or placebo may be interrupted as described below. Patients are to be instructed to notify investigators at the first occurrence of any adverse sign or symptom.

Patients experiencing the following adverse events should have their treatment interrupted:

- Jaundice or deterioration in liver function
- Significant increase in blood pressure
- New onset of migraine-type headache

Treatment may be held as needed until toxicity resolution. Appropriate follow up assessments should be done until adequate recovery occurs as assessed by the Investigator. Treatment will be resumed once this toxicity completely disappeared; if treatment cannot be resumed within 3 weeks it will be interrupted permanently.

All dose interruptions must be clearly documented in the patient's source notes and in the eCRF.

##### **5.4.2 Special conditions**

The following conditions will require a closer revision of the investigator:

- Heart disease or circulation problems
- Hypercholesterolemia

- Hyperglycemia
- Breast changes
- Uterine fibroids or endometriosis
- Epilepsy
- Asthma
- Systemic Lupus Erythematosus
- Otosclerosis

### 5.5 Medication Errors and Overdose

Medication errors may result in this study from the administration at the wrong time. Such medication errors occurring to a study participant are to be captured on the eCRF. In addition the Sponsor should be notified immediately.

Medication errors are reportable irrespective of the presence of an associated AE/SAE, including:

- ✓ Medication errors involving patient exposure to the product;
- ✓ Potential medication errors or uses outside of what is foreseen in the protocol that do or do not involve the participating patient.

### 5.6 General Concomitant Medication and Supportive Care Guidelines

Patients must be instructed not to take any additional medications (over-the-counter or other products) during the study without prior consultation with the investigator. Any medications including herbal supplements, vitamins, or treatment taken by the patient from 28 days prior to the start of study treatment and up to 30 days ( $\pm 5$  days) following the last dose of investigational product and the reason for their administration must be recorded on the eCRF.

Routine postoperative care, such as dressing changes, suture removal, drain removal, or venous access (central or peripheral), does not need to be recorded. Anesthetics used for any surgical procedures performed during the patient's participation in the study can be recorded as "unspecified anesthesia" on the concomitant treatment records; it is not necessary to list the specific anesthetics.

#### 5.6.1 Prohibited Medications

The following treatments are prohibited throughout the duration of the active treatment phase:

- ✓ **Anticancer agents:** No additional investigational or commercial anticancer agents such as chemotherapy, immunotherapy, targeted therapy, biological response modifiers or endocrine therapy (different than the NSAI: anastrozole or letrozole) will be permitted during the active treatment phase. In general, any drugs containing "for the treatment of breast cancer" on the product insert are not permitted on study.

- ✓ **Hormone replacement therapy with estrogens or progestins, tibolone**, topical estrogens (different from the study drug/placebo), phytoestrogen, **megestrol acetate** and **selective estrogen-receptor modulators** (eg, raloxifene, tibolone) are prohibited during the active treatment phase.

### 5.6.2 *Permitted Medications*

The following treatments are permitted throughout the duration of the active treatment phase:

- ✓ **Standard therapies** for pre-existing medical conditions, medical and/or surgical complications, and palliation. Any medication intended solely for supportive care (eg, analgesics, antidiarrheals, antidepressants) may also be used at the investigator's discretion. All medications should be recorded.
- ✓ **Bisphosphonates and receptor activator of nuclear factor kappa-B ligand (RANKL) inhibitors** for the treatment of osteopenia/osteoporosis.

## 5.7 Treatment Compliance

The compliance will be evaluated by the Investigator Team at week 3, 8 and 12 by counting and recording the number of unused applicators returned in each period.

The percentage of pharmacological compliance will be calculated from the count of the applicators.

To evaluate the compliance, the flexibility permitted in the appointments, having to increase or reduce applicators from the theoretical calculation of applicators returned, will be taken into consideration. Checking the patient completion calendar will facilitate this evaluation.

## 5.8 Blinding and Unblinding

The study drug, 0.005% Estriol vaginal gel, and its vehicle in gel (placebo vaginal gel) will be of identical appearance and will have the same aroma and the same texture in order to maintain the double blind.

Throughout the study, the medication with which the patient is being treated will be kept strictly confidential and only authorized persons will have access to this information, unless it is necessary to break the blinding due to safety reasons. The unblinding must be done only by the principal investigator of the site or by an authorized person, only when the knowledge of the treatment assignment is deemed essential for the patient's care.

The randomization codes will be unblinded and made available for the project statistician to perform the data analysis, when the study has been finalized, the database has been verified and the protocol violations have been determined. All personnel involved directly in the study shall be unaware of the treatment assigned to the patients until the database has been closed.

### **5.8.1 Process for urgent unblinding**

In general, unblinding of participants during the conduct of the clinical trial is not allowed unless there are compelling medical or safety reasons to do so.

Any serious adverse event considered by the investigator to be related to the blinded treatment medication (0.005% estriol vaginal gel/placebo vaginal gel) should be reported as such to the sponsor via the appropriate SAE reporting form.

There will be two complete sets of randomization codes. One will be kept by the GEICAM Pharmacovigilance department and the other will be distributed among the investigators. The emergency codes should be kept in a safe but accessible place in the event they should be opened. Each investigator will receive the necessary envelopes closed to randomize a determined number of patients. Each envelope will contain the details of the treatment that the patient is receiving. In the case of emergency the envelope must be opened to determine the treatment being administered.

The randomization envelopes can only be opened in an emergency. When the investigator opens the envelope he/she must record the date, the time and the reason he/she has had to do so and will keep this information with the eCRF documentation. He/she should also immediately inform the study monitor that a treatment code has been opened. As per regulatory reporting requirement, it will unblind the identity of the study medication for all unexpected SAES that are considered by the investigator to be related to the study drug. Details of subjects who are unblinded during the study will be included in the Clinical Study Report.

---

## **6. Efficacy and Safety Evaluations, Sample Collection and Testing (Standard Laboratory Testing) and Appropriateness of Assessments**

Study procedures and their timing (including tolerance limits for timing) are summarized in the Study Schedule, Protocol Attachment 1.

Patients will receive the treatment for 12 weeks (3 months).

Patients will be evaluated at baseline (within 2 weeks prior to treatment initiation on day 1), at week 1 (day 8 +/- 2 days) at week 3 (day 22 +/- 3 days), week 8 (day 57 +/- 3 days) and week 12 (day 85 +/- 3 days). There will be an additional safety visit 4 weeks ( $\pm$  5 days) after the last study medication administration.

Before a patient starts her participation in the study, she must have given her written informed consent. Through this consent, it is guaranteed that the person voluntarily expresses their wish to participate in the clinical trial, after having understood all the information that has been provided to her about the study.

### **6.1 FSH serum levels**

The primary endpoint is to evaluate the variation of FSH levels in serum from baseline to 12 weeks of treatment with 0.005% estriol vaginal gel. As a secondary endpoint, we will evaluate the variation at different time points along 8 weeks of treatment with 0.005% estriol vaginal gel.

Blood samples to analyze FSH (in serum) will be collected at six time points:

- Screening: one blood extraction
- Baseline visit: one blood extraction.
- Weeks 1-3: one blood extraction in visits at week 1 (day 8 +/- 2 days) and week 3 (day 22 +/- 3 days).
- Weeks 4–12: one blood extraction in visits at week 8 (day 57 +/- 3 days) and week 12 (day 85 +/- 3 days).

Serum FSH levels will be determined in a Central Laboratory (Laboratorios Echevarne). Chemiluminescent assay will be used for their analysis.

Detailed instructions for the collection, labelling, handling and shipment of samples are outlined in the Sample Management Manual.

### **6.2 Estriol, estradiol, estrone plasma levels and LH serum levels**

Secondary endpoints are to evaluate the variation of estriol, estradiol and estrone levels in plasma and LH levels in serum along 12 weeks of treatment with 0.005% estriol vaginal gel.

Blood samples to analyze LH (in serum) will be collected at the same six time points:

- Screening: one blood extraction

- Baseline visit: one blood extraction
- Weeks 1-3: blood extraction in visits at week 1 (day 8 +/- 2 days) and week 3 (day 22 +/- 3 days)
- Weeks 4–12: blood extraction in visits at week 8 (day 57 +/- 3 days) and week 12 (day 85 +/- 3 days)

Blood samples to analyze estriol, estradiol, estrone (in plasma) will be collected at five time points:

- Baseline visit: one blood extraction
- Weeks 1-3: blood extraction in visits at week 1 (day 8 +/- 2 days) and week 3 (day 22 +/- 3 days)
- Weeks 4–12: blood extraction in visits at week 8 (day 57 +/- 3 days) and week 12 (day 85 +/- 3 days)

Plasma estradiol, estriol, estrone levels and serum LH levels will be determined in Central Laboratories (Laboratorios Echevarne; Pharm-Analyt). Due to the extremely low levels of plasma estrogens expected, a newly developed and validated ultrasensitive LC-MS/MS assay will be used for the analysis of estradiol, estriol and estrone at Pharm-Analyt. Chemiluminescent assay will be used for the analysis of Serum LH at Laboratorios Echevarne.

Detailed instructions for the collection, labelling, handling and shipment of samples are outlined in the different Sample Management Manuals.

### **6.3 Safety assessments**

Investigators are responsible for monitoring the safety of patients who have entered this study and for alerting GEICAM to any event that seems unusual.

The investigator is responsible for appropriate medical care of patients during the study.

The investigator remains responsible for following, through an appropriate health-care option, adverse events that are serious or that caused the patient to discontinue before completing the study. The patient should be followed until the event is resolved or explained. Frequency of follow-up evaluation is left to the discretion of the investigator.

During the course of the study, all patients entering the trial must be evaluated according to the schedule outlined in the flow charts and described below. The results of the evaluation will be recorded in the eCRF pages until the patients are not followed anymore.

#### **6.3.1 Timing of Assessments**

Physical and gynecological examination including vital signs assessments (blood pressure and pulse), will be performed at screening, week 1 (day 8 +/- 2 days), week 3 (day 22 +/- 3 days), week 8 (day 57 +/- 3 days), week 12 (day 85 +/- 3 days) and 4 weeks after the last study drug

administration. Height and weight will be registered at screening. Gynaecological examination will comprise breast examination and pelvic examination (examination of uterus and appendages), and will be performed at baseline and at weeks 3 and 12. Endometrial ultrasound will be performed at screening and at week 12.

The following safety laboratory assessments will be performed by the local laboratories, at screening and at week 12 and 4 weeks (+/- 5 days) after the last study drug administration:

- Hematology: hemoglobin, WBC, absolute neutrophils, platelet count.
- Blood Chemistry: fasting glucose, alkaline phosphatase, ALT, AST, total bilirubin, serum creatinine and BUN (or urea).
- Urine test: density, pH, glucose, proteins, cetones, bilirubin, blood, nitrites, urobilinogen and leukocytes.

All AEs (and their relatedness to the study drug) occurring during the study will be documented in the eCRF at baseline, week 1 (day 8 +/- 2 days), week 3 (day 22 +/- 3 days), week 8 (day 57 +/- 3 days), week 12 (day 85 +/- 3 days) and 4 weeks after the last study drug administration. AEs will be graded according to MedDRA for each type of adverse event will be recorded. Additionally, the relationship of the adverse event(s) to the study treatment will be taken into consideration.

### 6.3.2 Safety Definitions

The safety definitions are described in the table 2.

**Table 2:** Safety definitions

Concept	Definition
Adverse Event (AE)	
Any new untoward medical occurrence or worsening of a pre-existing medical condition in a patient or clinical investigation subject administered an investigational (medicinal) product and that does not necessarily have a causal relationship with this treatment.
 
An AE can therefore be any unfavorable and unintended sign, symptom or disease temporally associated with the use of investigational product, whether or not considered related to the investigational product.
 
Laboratory abnormalities should be reported as AE only in case they lead to an action on study treatment or if they are serious.

Adverse Reaction (AR)	
All untoward and unintended responses to a medicinal product related to any dose administered.
 
All expected ARs are listed in the Summary of Product Characteristics [SmPC]. If the nature or the severity of an

adverse reaction is not consistent with the applicable product information, the AR is defined as unexpected. The basis for the decision is the current version of the corresponding reference document that has been submitted and approved by the competent authority and the ethics committees.

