**Study Design and Treatment:**

This is a phase II, prospective, randomized, double-blind, placebo-controlled, international (Spain and Sweden) and multicentre study.

60 patients will be randomized to receive 0.005% estriol vaginal gel (arm A) and placebo moisturizing gel (arm B) in a 4:1 proportion, so 48 patients will enter in arm A and 12 in arm B.

**Arm A:** Investigational drug product: 0.005% estriol vaginal gel (Blissel®)

Route: Vaginal. Administration by an applicator inserted deep inside the vagina

Dose: 1 g of gel, containing 50 µg of estriol

Dosage schedule: Weeks 1-3: single daily application  
Weeks 4-12: twice weekly administration.

Women will be instructed to administer the gel at bedtime.

**Arm B:** placebo moisturizing gel administered in the same way.

Patients will have hormone determinations (estriol, estradiol, estrone, FSH and LH) analyzed in a central laboratory at baseline and at weeks 1, 3, and 8 from the beginning of the therapy and at week 12 (last day of study therapy). An additional FSH and LH determination will be obtained during the screening period in order to assess the intra-individual variation of these hormones in baseline conditions. Patients will also undergo gynaecological examination (vaginal smear and pH), evaluation of vaginal symptoms and signs, and will answer a female sexual function questionnaire at baseline, at week 3 (from the beginning of therapy) and week 12 (last day of study therapy). Adverse events will be followed along the study and specifically collected at weeks 1, 3 and 8 from the beginning of therapy, at week 12 (last day of study therapy) and at safety visit (30 ±5 days after last day of study therapy).

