## 4.3 Discontinuations

### 4.3.1 *Discontinuation of Study Medication*

The criteria for enrollment must be followed explicitly. If a patient who does not meet enrollment criteria is inadvertently enrolled, that patient should be discontinued from the study medication, an exception may be granted if the patient, in the opinion of the investigator, is having benefit from the study medication. In these rare cases, the investigator must obtain documented approval from the sponsor to allow the patient to continue to receive the study drug.

Patients can be discontinued from the study therapy in the following circumstances:

- Patient's own request.
- Unacceptable toxicity.
- Tumor recurrence.
- Any clinical adverse event (AE), laboratory abnormality or inter-current illness which, in the opinion of the investigator, indicates that continued participation in the study is not in the best interest of the patient.
- Termination of the study by the sponsor.
- Physician's decision, including need of other anti-cancer therapy, not specified in the protocol.
- If the patient is non-compliant with study procedures.
- Loss of ability to freely provide consent through imprisonment or involuntarily incarceration for treatment of either a psychiatric or physical (e.g. infectious disease) illness.
- All patients will be discontinued from the treatment phase and they will perform the safety visit in case of a delay of more than 1 week during the daily administration phase or more than 2 weeks during the twice weekly administration phase, or permanent discontinuation of the study drug unless there is an obvious clinical benefit per the investigator's medical judgment and after discussion with the sponsor.

If possible, and after the permanent discontinuation of treatment, the patients will be assessed using the procedure normally planned for the last dosing day with the study treatment.

All permanent treatment discontinuation should be recorded by the Investigator in the eCRF when considered as confirmed.

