
Serious Adverse Event (SAE) and Serious Adverse Reaction (SAR)
	
Any adverse event or adverse reaction that, at any dose:
 
 
○ is fatal (results in death),
 
○ initial or prolonged inpatient hospitalization,
 
○ a life-threatening experience (that is, immediate risk of dying, defined as an event in which the patient was at risk of death at the time of the event; it does not refer to an event which hypothetically might have caused death if it were more severe),
 
○ persistent or significant disability/incapacity,
 
○ congenital anomaly/birth defect or
 
○ an important medical event, defined as a medical event that may not be immediately life-threatening or result in death or hospitalization but, based on appropriate medical and scientific judgment, may jeopardize the patient or may require intervention (eg. medical, surgical) to prevent one of the other serious outcomes listed above.
 
 
Do not confuse the concept “serious”, described before, with “severe” which refers to the intensity of the AE or AR (minor/mild/severe).
 
Any temporary increase in the severity of a symptom or previous sickness that happens after the baseline of the study is considered also as an adverse event.

Suspected Unexpected Serious Adverse Reaction (SUSAR)
	
Any serious adverse reaction whose nature, intensity or consequences do not correspond with the reference information for the investigational product (Summary of Product Characteristics [SmPC]).
 
The unexpected nature of an adverse reaction is based in the fact of not being observed previously and not in what could be advanced based on the pharmacological properties of the drug.

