### Protocol Attachment 1. Study Schedule

Study Schedule of Events and Timelines. ITFE-2026-C10 (BLISSAFE Study)	During Study Treatment. All visits (except week 1) +/- 3 days of scheduled treatment day.	Post-treatment (4 weeks) from the last study drug dose
---	--	---

Visits	Screening	Baseline	Week 1	Week 3	Week 8	Week 12 or early withdrawal visit	Post-treatment (4 weeks) from last study drug dose	
Day	Within 14 days prior to the registration	1 o	8 (+/- 2 days)	22 (+/-3d)	57 (+/-3d)	85 (+/- 3d)	+30 (+/-5d)	
Procedure/Laboratory/ Diagnostic Test								
ICD for Entry (before any study specific tests) a	X							
Medical and surgical history and demographics b	X							
Physical examination c	X		X	X	X	X	X	
ECOG PS	X		X	X	X	X	X	
Hematology d	X					X	X	
Blood Chemistry e	X					X	X	
Urine Test f	X					X	X	
Endometrium by transvaginal ultrasound g	X					X		
Moderate or severe vaginal dryness	X							
Review Inclusion/Exclusion Criteria	X	X						
Concomitant medications	X	X	X					

Visits	Screening	Baseline	Week 1	Week 3	Week 8	Week 12 or early withdrawal visit	Post-treatment (4 weeks) from last study drug dose
Day	Within 14 days prior to the registration	1 o	8 (+/- 2 days)	22 (+/-3d)	57 (+/-3d)	85 (+/- 5d)	+30 (+/-5d)
AEs and SAEs h	X	X	X				
Blood (serum) samples for FSH and LH determination i	X	X p	X	X	X	X	
REGISTRATION / RANDOMIZATION		X					
Blood (plasma-EDTA) samples for estriol, estradiol and estrone determination i		X p	X	X	X	X	
Gynaecological examination j		X p		X		X	
Symptoms and signs of vaginal atrophy k		X p		X		X	
Measurement vaginal pH l		X p		X		X	
Vaginal cytology sample to evaluate the vaginal Maturation Value m		X p		X		X	
FSFI questionnaire n		X p		X		X	
Study drug/ placebo dosing n		X n	X n				

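### The main study's safety panels are drawn at or after the end of dosing, so for them the laboratory-AE rule is in effect serious-only

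*Protocol*

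**What the plan says.** **Reporting rule.** Protocol section 6.3.2, Table 2: "Laboratory abnormalities should be reported as AE only in case they lead to an action on study treatment or if they are serious". The seriousness criteria in the same table include important medical events, meaning those that "may jeopardize the patient or may require intervention" to avert one of the listed serious outcomes.

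**When the tests are done.** Section 6.3.1 has the local laboratories run haematology, chemistry and urine "at screening and at week 12 and 4 weeks (+/- 5 days) after the last study drug administration". In Attachment 1 the end-of-treatment column is headed "Week 12 or early withdrawal visit", and no safety panel is marked at weeks 1, 3 or 8.

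**Where those visits fall relative to dosing.** The Summary, under Study Design and Treatment, ties the visit to the end of dosing: "at week 12 (last day of study therapy". For early withdrawals, section 4.3.1 says that, where possible, "after the permanent discontinuation of treatment, the patients will be assessed using the procedure normally planned for the last dosing day".

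**Interruption rule.** Section 5.4.1: "Patients experiencing the following adverse events should have their treatment interrupted". The first item listed is "Jaundice or deterioration in liver function".

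**Analysis.** Section 8.2.8 summarises adverse-event incidence overall and by investigator-assessed relationship, and compares adverse events between arms. It separately assesses haematological and biochemical toxicity from the laboratory values.

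**The concern.** A rule that depends on a treatment action can work when tests are done while treatment continues. Here the protocol pairs it with a schedule that puts every post-screening safety panel at the point where dosing stops, or later. One of the two routes into the adverse-event record is then nearly closed, for a reason unrelated to the medical importance of the finding. Whether a result is an adverse event would depend on the day it was drawn.

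What is at stake is the adverse-event record of a trial whose title gives safety as its purpose. A tabulated laboratory value carries no investigator judgement of relationship and does not enter the between-arm comparison of adverse events. An analysis plan cannot recover events that sites were told not to report.

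**Working it through.** The protocol gives no figure to reproduce. The check is a comparison of the dosing calendar with the panel schedule, followed by the rule applied to one result at two times.

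**Inputs.** Daily application in weeks 1 to 3, then two per week in weeks 4 to 12, with Monday and Thursday as the example (section 5.1.1). Week-12 visit on day 85 ± 3 days (section 6). 60 main-study women, 48 on estriol and 12 on placebo (section 3.1).

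**Planned applications.** 21 + 2 × 9 = 39, if dosing ends on day 84. If it runs through day 85, the total is 40 when day 85 is a Monday or Thursday.

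**Applications left when the week-12 panel is drawn.** Take each of 7 possible weekdays for day 1 with each of 7 visit days (82 to 88), which gives 49 combinations. Count a bedtime dose on the visit day as coming after the draw.

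- Dosing to day 84: the last application falls on day 81 to 84. At a day-85 visit 0 are left for every start weekday. Over the window, 37 of 49 combinations leave 0 and the other 12 leave 1, so at least 38/39 = 97.4% of applications precede the draw.
- Dosing to day 85: at most 1 is left at a day-85 visit. Over the window, 30 of 49 combinations leave 0 and the maximum is 2, so at least 38/40 = 95.0% precede the draw.
- One part of the Attachment 1 table prints ± 5 days for week 12. With dosing to day 84, the maximum left is then 2.

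**Other panels.** 0 are left at the safety visit, and 0 at an assessment made after permanent discontinuation.

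**Extent.** 60 × 2 = 120 planned panels if every woman has both. The hormone draws at weeks 1, 3 and 8 (60 × 3 = 180) fall during dosing and are not affected.

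**The same result at two times.** Take a non-serious, symptom-free rise in liver enzymes that amounts to deterioration in liver function.

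- Found by an unscheduled test in week 6: section 5.4.1 requires interruption. Interruption is an action on treatment, so Table 2 makes the rise an adverse event. It enters the incidence, relationship and between-arm outputs.
- Found in the week-12 panel with no dose left, or at the safety visit: there is nothing to interrupt and the finding is not serious. Table 2 excludes it, and only the value reaches the laboratory assessment.

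**Number of findings.** The document gives no rate. Purely as an assumption, if 1% to 10% of women had such a finding, 60 × 0.01 = 0.6 to 60 × 0.10 = 6 women would be affected, of whom 0.1 to 1.2 would be among the 12 on placebo. This range only gives a sense of scale.

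**The case against.** The strongest defence is that the rule is explicit and forms half of a coherent design: isolated non-serious values stay out of the adverse-event listing and are assessed as laboratory data under section 8.2.8. The remaining gap is also narrow. A diagnosis or symptom behind a value is still an adverse event, the important-medical-event criterion already lets in medical judgement, and section 6.3 asks investigators to alert the coordinating group to anything unusual. All of that stands, and it keeps the point small. It does not explain why an identical result should count in week 6 and not in week 12.

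A reader might infer stronger things that the protocol does not support:

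- **That Table 2 contradicts section 5.4.1.** It does not. Section 5.4.1 is a dosing instruction. While doses remain, following it makes the finding reportable under Table 2; once dosing has ended it directs nothing and Table 2 alone governs. Calling the listed items adverse events does not turn it into a reporting rule, so there is also no basis for predicting that sites will report differently.
- **That laboratory findings are lost.** Sections 6.3 and 8.2.8 have results recorded in the eCRF and toxicities assessed from the values.
- **That the hormone results are compromised.** The primary and secondary hormone analyses use measured levels and do not depend on adverse-event reporting.
- **That a given number of events will be missed.** Nothing in the document allows such an estimate.

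**Conclusion.** The point holds as a poor fit between a reporting rule and the trial's own schedule. For the main study's post-screening haematology, chemistry and urine panels, the treatment-action route is practically closed and seriousness is the only one left. Non-serious abnormalities that would have been adverse events during dosing drop out of the incidence, relationship and between-arm outputs.

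This rests on reading week 12 as the end of dosing, as the Summary does, and on the planned schedule being followed. A visit early in the window leaves at most 1 or 2 applications, which does not change the conclusion. The claim does not extend to unscheduled tests during dosing or to the 10 safety-phase women. The effect is probably small and severity is low; the point is worth making because the correction is cheap and safety is the trial's stated purpose.

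**What to change.** Amend the laboratory sentence in Table 2 of section 6.3.2. Keep the two existing routes and add that a new or worsened laboratory abnormality is also an adverse event when the investigator judges it clinically significant, or when it would have required interruption under section 5.4.1 had dosing continued, whether or not any dose remains. Carry the wording into the eCRF guidance for the week-12, early-withdrawal and safety visits.

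The cost is a few more adverse-event entries and queries, and some reliance on investigator judgement across about 5 sites. A grade threshold would be more objective, but section 6.3.1 speaks of grading by MedDRA and section 6.3.3 of CTCAE grades, so that would have to be settled first. No new visit, sample or test is needed.
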